5.2. Change in care pathway/referral plan

Number and proportion of consultation with a change in care pathway / referral plan (Q26).

Visual support : Table (continuation of the table 5.1)

- Number and proportion of consultations with a referral for each category of referral before and after POCUS examination (Q13, Q27)
- Change in referral to emergency departments (Relative risk, 95% CI, Mac Nemar test)

We will group referrals to hospital and specialist in semi-emergency in a category “semi-urgent referral”, and hospital and specialist in the context of non-emergency in a category “non-urgent referral”.

5.3. Change in imaging prescription

We will consider there is a change in imaging prescription if there is a prescription of different imaging modalities before and after POCUS.

Visual support : Table (continuation of the table 5.1)

- Number and proportion of consultations with a prescription of each kind of imaging modality before and after POCUS examination (“Radiography”, “Echography”, “IRM”, “TDM”, “Other imaging”) (Q13, Q27)
- Change in imaging prescription, regardless of the type of imaging (Relative risk, 95% CI, Mac Nemar test)

Visual support : Table

- Number and proportion of consultations with an increase in imaging prescription after POCUS examination, and a decrease in imaging prescription for each imaging modality.

- Number and proportion of consultations with a final imaging prescription while none were prescribed initially.
- Number and proportion of consultations with an initial imaging prescription while none were prescribed finally.

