General practitioners will be selected by random draw from among eligible respondents.

From the responding physicians, we will recruit 60% who practice in the Île-de-France region. If the number of interested physicians in Île-de-France proves insufficient, recruitment may be expanded to other regions of France, giving priority to geographic diversity.

Similarly, if initially recruited physicians fail to participate, recruitment may be extended to eligible physicians from other regions of France to ensure an adequate number of patient inclusions for the study.

c. Sample size

According to the data from a pilot study, POCUS is used for 5 to 7% of GP consultations, which corresponds to 1 or 2 POCUS for 25 consultations(14). During the 22-day inclusion period, we expect that every GP performs between 22 and 44 POCUS exams, which makes an expected total of 660 to 1,320 POCUS. We estimate that 70% of the POCUS performed can be included. The number of investigators planned is comparable to the Danish study in which 20 GPs participated and approximately 600 POCUS exams (30 ultrasounds / doctor) were completed during the inclusion period which lasted 1 month. The total number of POCUS expected is sufficient for a valid statistical description.

d. Inclusion criteria

The GPs must fulfil the following criteria:

- minimum use of POCUS on two anatomical areas
- GP activity for minimum two days / week
- A minimum of two scanning probes
- Previous participation in formal education in the use of POC-US
- Minimum six-month experience with POCUS in general practice.
- Estimated use of POCUS on a daily basis (average)

e. Exclusion criteria

GPs will be excluded from the study in the following situations :

- Conflict of interest involving the participating physician
- Participation in the research group or scientific advisory board
- Direct financial interest in the sale or promotion of ultrasound devices
- Inclusion of fewer than 5 patients, assessed at the end of data collection
- Exclusive practice of scheduled ultrasounds only (i.e., ultrasounds performed during dedicated, pre-planned consultations specifically arranged for that purpose, whether or not requested by another practitioner)
- Change in professional activity between recruitment and the start of patient inclusion (e.g., stopping the practice of general practice or discontinuing the use of POCUS)

f. Ultrasound Training of Investigator Physicians

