- Day 14 appointment : To review progress, confirm that recruitment is proceeding smoothly, and verify initial data collection, as well as detect any errors, duplicates, or issues.
- End-of-inclusion appointment : To review any difficulties faced, discuss the number of patients enrolled and excluded, and provide information regarding the documents to be sent back, those to be retained, and their retention duration.

f. Data coding

The physicians' diagnostic hypotheses will be entered as free-text responses in the questionnaire.

To facilitate epidemiological analysis and standardize the data, these diagnoses will be translated into coded data using the International Classification of Primary Care, 2nd edition (ICPC-2). This is the French version of the classification system developed by the World Organization of Family Doctors (WONCA).

g. Statistical analysis

- Descriptive analyses

Descriptive analyses will be performed using RStudio software. For quantitative data, most will be summarized using means and standard deviations if they follow a normal distribution, and medians and interquartile ranges if they do not. Qualitative data will be expressed as percentages. Bar charts will be created to represent the various organs examined by the physicians.

- Comparative analyses

Statistical comparative analysis will be conducted using RStudio software.

For these analyses, we will exclude patients for whom the POCUS time recorded on SurveyXact is less than 60 seconds between completing the first questionnaire and the second. We will consider that there was no response before and after, only an "after ultrasound" response.

Data collection will primarily rely on nominal variables. Categorical variables will be described using contingency tables.

To assess the relationship between paired variables, we will use the Mac Nemar test. To compare the characteristics of included and excluded patients, we will use a Chi-2 test. Results will be considered statistically significant if the p-value is less than 0.05. For highly significant results with p-values much lower than 0.05, we will simply report $p < 0.01$.

h. Ethics

This study falls under the Jardé law and qualifies as a Category 3 study. This is an observational, non-interventional study, and the procedure under investigation (POCUS) is used in the "usual practice", without altering the management of study participants. In accordance with the General Data Protection Regulation (GDPR), a MR004 compliance

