3.2.1. Questionnaire BEFORE POCUS

Question Number	Question	Possible Answers	Answer format
Q1	GP ID Number	A à Z or AA à AM	1 or 2 letters
Q2	Patient ID number	A1 to Z26 and AA1 to AM26	1 or 2 letters follow by 2 digits
Q3	Date	2022-11-17 to 2024-06-06	AAAA-MM-JJ
Q4	Patient gender	Man, Woman or Other	Single answer question
Q5	Patient Age	0 to 120	Number with 1 to 3 digits
Q6	Setting of POCUS	
- At patient's home- At medical office- Other, to specify	Single answer question
Q7	What is the main reason to use POCUS in this patient ?	
- Answer to a specific clinical question (answer yes/no/maybe) and document the answer in patient's medical record- Therapeutic Education- Follow or Control an echographic	Multiples answers question

		
signal
 
 - Screen an asymptomatic patient - Training without clinical benefit - Analyse and describe in detail an anatomical structure with multiples organs and edit a complete report 	
Q8	Anatomical areas planned to be scanned	
 - Abdominal/Urologic - Gynecologic-Obstetrical - Musculoskeletal - Vascular - Thoracic - Other/Superficial 	Multiples answers question
Q9	Organs planned to be scanned	
 - Gallbladder, Kidneys, Liver, Spleen, Pancreas, Morrisson's pouch, Bladder, Prostate, Testes, Douglas pouch, Other abdominal structures - Uterus, Ovaries, Gestational sac, Embryo, Douglas pouch, Other gynecological/obstetric structures - Joint, Joint infiltration, Muscle, Tendon, Bone, Other musculoskeletal structures - Aorta, Deep veins of the lower limbs, Carotid arteries, other vascular structures - Lungs, Pleura, Heart, Other thoracic structures - Thyroid, Tissues, Lymph nodes, Breasts, Other superficial structures 	Multiples answers question
Q10	What is the main tentative diagnosis for this patient ?	ICPC2 code	1 letter followed by 2 digits
Q11	Are there any other possible tentative diagnoses in this case ?	Yes / No	Single answer question
Q12	Second, Third and Fourth tentatives diagnoses	ICPC2 code	1 letter followed by 2 digits

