4.3. Patients's characteristics

Visual support : Flow Chart

- Number of patients eligibles for a POCUS
- Number of patients excluded by GPs, exclusion criteria described
- Number of patients included in the study
- Number of patients excluded after data verification, exclusion of data errors

- Number of patients included in analysis
- Number of patients excluded because of an ultrasound duration of less than 60 seconds
- Number of patients included in “pre-post” analysis
- The difference for age and gender between the excluded patients by GPs according to the exclusion criteria and the included patients in the study will be tested by chi2 test.

Visual support : Table

- Gender : Number and proportion of patients
- Age : médian/interquartile
- Place of performing POCUS : number and proportion of patients per group (“medical office”, “patient’s home”, “other”)
- Geographic region of performing POCUS : Number and proportion of patients per region
- Number of patients included per GP : Median/interquartile

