5.4. Change in treatment plan

Number and proportion of consultations with a change in treatment plan (Q28).

Visual support : Table (continuation of the table 5.1)

- Number and proportion of consultations with a prescription for each treatment category before and after POCUS examination (Q14, Q29)
- Change in prescription of overall treatment (relative risk, 95% CI, Mac Nemar test)

Non-medical treatments included physiotherapist, podiatrist and osteopath.

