5.6. Global change in patient care

We will consider a global change if there was a change in the main hypothesis, a global change in diagnostic hypotheses, a change in treatment plan, in patient's orientation plan or in imaging or exams prescription.

Visual support : Table (continuation of the table 5.1)

Number and proportion of consultations with a global change in patient care.

For all comparative analyses, we will consider consultations with a measured POCUS duration greater than 60 seconds.

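### SAP 5.3 and 5.4 (and, with less effect, 5.2) calculate before/after intervals and McNemar tests as if consultations were independent, although patients are nested in GPs

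*SAP*

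**What the plan says.** Three SAP sections make a before/after inference, all in the same form:

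- 5.3, imaging: "Change in imaging prescription, regardless of the type of imaging (Relative risk, 95% CI, Mac Nemar test".
- 5.4, treatment: "Change in prescription of overall treatment (relative risk, 95% CI, Mac Nemar test".
- 5.2, emergency referral: "Change in referral to emergency departments (Relative risk, 95% CI, Mac Nemar test".

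The protocol's statistical analysis section (VI.g) says "To assess the relationship between paired variables, we will use the Mac Nemar test" and sets significance at 0.05. SAP 5.6 defines the analysis set: "For all comparative analyses, we will consider consultations with a measured POCUS duration greater than 60 seconds".

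The GP's ID is the first item of the questionnaire (SAP 3.2.1). In the SAP's patient-level results, the grouping by GP appears only as a description in 4.3: "Number of patients included per GP : Median/interquartile". Neither document mentions an intraclass correlation, GEE, a mixed model, a robust variance or a GP-level bootstrap. The SAP does not name the formula for the relative-risk interval, nor the version of McNemar's test.

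**The concern.** The outcome is the GP's own decision, and the same GP writes down the plan before and after the scan for every patient he or she includes. GPs differ in training, equipment and experience, which SAP 4.1 and 4.2 tabulate. Some may mainly drop imaging after a scan while others mainly add it. Changes from one GP would then be correlated. McNemar's test and a paired relative-risk interval both count each consultation as an independent piece of evidence, so they would overstate precision.

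At stake are the three sets of intervals and p-values that the SAP plans for the therapeutic role of POCUS, which is a stated aim of the study.

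**Working it through.** **Inputs from the documents.** Protocol II.c expects 22 to 44 examinations per GP, 660 to 1,320 in total, with 70% includable.

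- GPs: 660/22 = 1,320/44 = 30. The protocol does not state this number; it is back-solved. The SAP's GP codes run A-Z and AA-AM, so 26 + 13 = 39 codes. That is not a stated enrolment figure either.
- Included patients: 0.7 × 660 = 462 to 0.7 × 1,320 = 924.
- Per GP: 462/30 = 15.4 and 924/30 = 30.8; 462/39 = 11.8 and 924/39 = 23.7. The patient ID format is "A1 to Z26 and AA1 to AM26", so 26 replaces 30.8 as a working value.

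The cells are therefore 30 GPs × 15 or 26 patients and 39 GPs × 12 or 24.

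**Inputs assumed.** q is the share of consultations whose before and after answers differ (5, 10 or 30%). s is the between-GP SD of the probability that a changed plan is an addition (0, 0.1 or 0.2, mean 0.5). Before-POCUS prevalence is 6, 12 and 40% for q = 5, 10 and 30%.

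**Formula at the null.** Score each consultation +1 (added), −1 (removed) or 0. Its variance is q, and the GP-level mean has variance (2qs)² = 4q²s². So ICC = 4q²s²/q = 4qs², design effect DE = 1 + (m − 1) × ICC for m patients per GP, and true size = 2 × [1 − Φ(1.96/√DE)].

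For q = 0.30 and s = 0.2, ICC = 4 × 0.30 × 0.04 = 0.048. The last two columns are from simulation, 20,000 runs per cell:

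| GPs × patients | DE | √DE | Size, formula | Size, simulated | Paired RR interval coverage |
|---|---|---|---|---|---|
| 30 × 15 | 1 + 14 × 0.048 = 1.672 | 1.29 | 13.0% | 13.3% | 86.7% |
| 30 × 26 | 1 + 25 × 0.048 = 2.200 | 1.48 | 18.6% | 18.5% | 81.5% |
| 39 × 12 | 1 + 11 × 0.048 = 1.528 | 1.24 | 11.3% | 11.2% | 88.8% |
| 39 × 24 | 1 + 23 × 0.048 = 2.104 | 1.45 | 17.7% | 17.5% | 82.5% |

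Repeat simulations agree to within about one percentage point. The paired SE of log RR is √((b + c)/(x1·x2)), where b and c are the removals and additions and x1 and x2 are the numbers with the item before and after.

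**Other values** (same four cells, simulated):

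| s | q | McNemar size | With continuity correction | Paired coverage |
|---|---|---|---|---|
| 0.2 | 10% | 6.9-9.9% | 5.1-8.0% | 90.2-93.1% |
| 0.2 | 5% | 6.5-7.2% | 3.5-5.2% | 92.9-94.3% |
| 0.1 | 30% | 6.4-8.8% | 5.3-7.7% | not tabulated |
| 0.1 | 5-10% | 5.4-6.4% | 3.0-4.9% | not tabulated |
| 0 | any | 5% | not tabulated | 95% |

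With the continuity correction, size at s = 0.2 and q = 30% is 9.9-17.0%. With unequal clusters spread evenly over 5 to 26 patients, size is about 15% and coverage 85% at that setting. If the 60-second rule also removes 20% (assumed), these become 13% and 87%.

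**Variation in how often GPs change plans.** If direction is the same for all GPs and there is no net change, paired coverage stays at 94.9-95.3%. With a net decrease it does not. Take 40% with the item before, 20% removed and 6% added, so 26% after and RR = 0.26/0.40 = 0.65. If the share of plans changed then varies between GPs with SD 0.1, paired coverage is about 93-94%. Agreement on direction alone therefore does not clear the interval.

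**If the interval is not paired.** An independent-groups interval has SE √(1/x1 − 1/N + 1/x2 − 1/N), where N is the number of consultations. It ignores the pairing. At s = 0.2 it covers 98-100% when 5-10% of plans change. At q = 30% it covers 91-96% with a before-POCUS prevalence of 40-50%, and 83-90% with 20%.

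**GP-clustered version.** Let K be the number of GPs and let x1k and x2k be GP k's counts before and after. The variance of log RR is K/(K − 1) × Σ(x2k/x2 − x1k/x1)², used with t on K − 1 df. In the null simulations coverage was 94.4-95.5% in every cell. The clustered McNemar statistic (Σdk)²/Σdk², where dk is additions minus removals in GP k, had size 4.4-5.2%.

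**The case against.** The strongest reply is that the size is wholly assumed. The documents give no ICC, no rate of changed plans and no variation between GPs. An SD of 0.2 is strong variation: the middle 95% of GPs would range from 13% to 87% additions among changed plans. The plausible range runs from no error to a material one, and nothing in the documents places this study within it. That stands, and it limits the claim to a conditional one.

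The protocol also calls its analysis descriptive (Results IV), and no power calculation or decision rests on these p-values. With a large net change the test result would seldom alter. At RR 0.70, q = 30%, SD 0.2 and 30 × 15, plain McNemar rejects in 98% of runs and the clustered test in 93%. For a rare outcome there is little to repair: at q = 1-3% and SD 0.2, McNemar size is 4.7-6.7% and paired coverage 94.0-96.2%. These points lower the severity and put 5.2 last. They do not remove the defect, because the SAP chose to report intervals and p-values, and these should perform as labelled.

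A reader might infer three stronger things that the documents do not support:

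- **That clusters are bounded at 5 to 26 patients.** The exclusion for "Inclusion of fewer than 5 patients, assessed at the end of data collection" applies before the data-error and 60-second exclusions, the ID range is only an answer format, and the protocol's own upper expectation is 30.8 per GP.
- **That the intervals are certainly too narrow.** The formula is unstated, and an independent-groups interval would usually be too wide.
- **That the chi-square tests in SAP 4.3 and 5.1 share the fault to the same degree.** Nothing here was worked out for them.

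**Conclusion.** The omission is certain; its effect is conditional. For 5.3 and 5.4, a paired interval is too narrow if GPs differ in direction of change, or in frequency of change when there is a net change. The McNemar p-value at the null is too small only when direction varies. Under the assumed SD of 0.2 the error is material when 30% of plans change and modest when 10% do. At SD 0.1 the size of the test is about 5-9%, and with no variation between GPs there is no error.

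The harm falls mainly on the interval. Relative-risk point estimates, counts and proportions are unaffected. Severity is minor to moderate, because the study is mainly descriptive.

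**What to change.** Add to SAP section 5 that the before/after relative risks in 5.3 and 5.4, and in 5.2 for consistency, are estimated by log-link GEE or modified Poisson regression with two rows per consultation. The variance should be clustered on GP ID, with a small-sample correction and t on K − 1 degrees of freedom for K GPs. Take the p-value from that model or from a GP-clustered McNemar test. Both rows of a consultation belong to one GP, so this also covers the pairing and settles the unstated interval formula.

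The cost is one or two sentences and a few lines of R, with no new data. Compared with the nominal paired interval, the clustered one is about 2-4% wider where GPs do not differ. It is 27-54% wider at SD 0.2 with 30% of plans changed, where the nominal interval under-covers.

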5.4. Change in treatment plan

Number and proportion of consultations with a change in treatment plan (Q28).

Visual support : Table (continuation of the table 5.1)

- Number and proportion of consultations with a prescription for each treatment category before and after POCUS examination (Q14, Q29)
- Change in prescription of overall treatment (relative risk, 95% CI, Mac Nemar test)

Non-medical treatments included physiotherapist, podiatrist and osteopath.

5.5. Change according to anatomical areas

Number and proportion of consultations changed according to anatomical areas :

- Change in main diagnostic hypothesis
- Global change in diagnostic hypotheses
- Change in imaging prescription
- Change in treatment plan
- Change in care pathway / referral plan
- Global change in patient care

Visual support : Table.

We will describe the change in patient care by anatomical area for patients having a scan of a single anatomical area. If at least 2 anatomical areas were scanned in the same ultrasound, we will group these patients in a new category called “>1 anatomical area”.

5.6. Global change in patient care

We will consider a global change if there was a change in the main hypothesis, a global change in diagnostic hypotheses, a change in treatment plan, in patient's orientation plan or in imaging or exams prescription.

Visual support : Table (continuation of the table 5.1)

Number and proportion of consultations with a global change in patient care.

For all comparative analyses, we will consider consultations with a measured POCUS duration greater than 60 seconds.
